4.3. Handling Withdrawals and Missing Data

Missing data for the primary efficacy endpoint, efficacy endpoint for sensitivity analysis, and selected secondary efficacy endpoints will be imputed with the multiple imputation (MI) method described in Section 6.2.2. All other endpoints will be not be imputed for missing data unless otherwise specified.

Dates that have incomplete information (the month and year or just the year is available) will be estimated for the purpose of calculating variables that are dependent on time if necessary. Day will be estimated as the first day (01) of the month (if month and year of partial date are available) or middle (July 1) of the year (if only year is available), unless otherwise noted. The imputations for partial dates are only for calculation purpose. Original date variables will not be modified. Listings will list dates as collected.

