8.3. Adverse Events

An adverse event (AE) is any untoward medical occurrence in a patient administered a pharmaceutical product which does not necessarily have to have a causal relationship with this treatment.

For recording of AE, the study period is defined for each patient as the time period from signature of the informed consent form (ICF) to the end of the follow-up period or the early termination visit for patients who discontinued from the study for any reason. Any AE occurring on or after the first dose of study drug is considered a treatment-emergent AE (TEAE). All AE summaries will be conducted for TEAEs.

The following are considered protocol-defined adverse events of special interest (AESI) to be sent to the sponsor's Global Patient Safety and Pharmacovigilance (GPSP) Department for evaluation:

- ophthalmic-related adverse events of at least moderate severity, as determined by the investigator
- severe hypersensitivity reactions

All AEs will be coded using MedDRA. The incidence of AEs will be summarized using descriptive statistics by SOC and preferred term (PT). Each patient will be counted only once in each PT or SOC category for the analyses of safety.

Statistical Analysis Plan

Summaries will be presented for all AEs (overall and by severity), AEs determined by the investigator to be related to test IMP (ie, reasonable possibility) (defined as related or with missing relationship) (overall, overall by severity, serious AEs, and AESI), serious AEs, AESI, AEs causing discontinuation from treatment, AEs causing early termination from the study, injection site AEs, and AEs leading to death.

Listings of AEs, AESI, serious AEs, injection site AEs, and AEs leading to early termination will be presented separately.

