8.9. Concomitant Medications or Therapies

Concomitant therapies and medications, including medications that are taken on an as needed basis and occasional therapies, will be monitored during the study. Details of prohibited medications may be found in the study protocol. All concomitant medications will be coded using the WHO Drug Dictionary.

The incidence of concomitant therapies and medications will be summarized using descriptive statistics by therapeutic class category and preferred term. Patients are counted only once in each therapeutic class, and only once in each preferred term category. Concomitant therapies and medications will include all medications taken after the 1st dose of study drug administration up to the end of study as defined in the study protocol.

Similarly the prohibited medications will be summarized separately.

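### SAP 4.3's partial-date rule makes no exception for adverse events or medications, so an adverse event with unknown onset day in the first-dose month is classed as pre-treatment and left out of the summaries

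*SAP*

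**What the plan says.** SAP 4.3 sets out a single convention. Incomplete dates "will be estimated for the purpose of calculating variables that are dependent on time if necessary". If month and year are known, "Day will be estimated as the first day (01) of the month (if month and year of partial date are available"; otherwise the date is set to the year's midpoint: "or middle (July 1) of the year (if only year is available), unless otherwise noted". The collected date is not overwritten, and "Listings will list dates as collected".

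SAP 8.3 collects adverse events from consent: "the study period is defined for each patient as the time period from signature of the informed consent form (ICF". Treatment-emergent status is then a comparison with the first dose: "Any AE occurring on or after the first dose of study drug is considered a treatment-emergent AE (TEAE". The tables are restricted to that subset: "All AE summaries will be conducted for TEAEs".

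For medications, SAP 8.9 counts as concomitant "all medications taken after the 1st dose of study drug administration up to the end of study", and SAP 5.5 counts as prior anything taken before the first dosing day.

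None of SAP 5.5, 8.3 or 8.9 gives its own partial-date rule, and Protocol Sections 7.1.2 and 9.8.2 do not supply one. The exception that SAP 4.3 leaves room for is never used for these data.

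**The concern.** Setting a missing day to the 1st does little harm when computing months since fibromyalgia onset, where an error of a few weeks is negligible. It is unsuitable for a before-or-after comparison with a dose that can fall on any day of the month. An event recorded only as June, in a patient first dosed on 15 June, becomes 1 June. It is then not treatment-emergent and is missing from the incidence tables, although it may have begun after the injection.

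Occurrence of adverse events is a stated safety endpoint. SAP 8.3 resolves another kind of missing information the cautious way: an event with missing causality is counted as related. A missing onset day gets the opposite treatment.

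Partial dates are conceivable after dose 1. The next scheduled visit is day 29 ±7, adverse events are elicited there by an open question (Protocol 7.1.2), and injection-site reactions are captured from spontaneous reports (Protocol 7.9). A patient may therefore be recalling an onset several weeks back.

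**Working it through.** The documents give no figure to reproduce; this is date logic. It applies the SAP 4.3 rule and the SAP 8.3 definition to a range of possible first-dose dates.

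**Inputs.** Imputed day = 1st of the recorded month, or 1 July if only the year is known (SAP 4.3). Treatment-emergent if onset is on or after first dose (SAP 8.3). Treatment period: day 1 to day 113 (SAP Table 1). Assumed: first-dose dates spread evenly over the 1,096 calendar days from 1 June 2019 to 31 May 2022, and true onset equally likely on any day from the dose to the end of that month.

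**1. Direction of the day-missing branch.**
- Recorded month earlier than the dose month: imputed date is before the dose, which is correct.
- Recorded month later than the dose month: imputed date is after the dose, which is correct.
- Same month, dose on the 1st: the event counts as treatment-emergent, which is correct.
- Same month, dose on any other day: the event is always dated before the dose, whatever the truth.

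This branch can therefore remove a true treatment-emergent event but can never create a false one.

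**2. Share of dose dates affected.** The 1st precedes the dose unless the dose is on the 1st, which holds for 36 of the 1,096 dates: (1,096 − 36)/1,096 = 1,060/1,096 = 96.7%. Hand check for a 30-day month: 29/30 = 96.7%.

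**3. Share of true post-dose, day-missing events misclassified.** Weight each dose date by the days left in its month: 16,147/17,243 = 93.6%. Hand check for a 30-day month: the days left sum to 30 + 29 + … + 1 = 465, of which 30 belong to a dose on the 1st, so 435/465 = 93.5%.

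**4. Exposed part of the treatment period.** Mean days from dose to month end = 17,243/1,096 = 15.7, and 15.7/113 = 13.9%. This is a share of days, not of events.

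**5. Year-only branch.** 1 July precedes the dose for 549/1,096 = 50.1% of dose dates. For those, a true post-dose event in the same year is dated before treatment. For the other 547 dates, 1 July falls on or after the dose. A patient dosed in March whose event truly began in February would then be counted as treatment-emergent. This branch errs in both directions.

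**6. Medications.** A stop date recorded as June in a patient dosed on 15 June becomes 1 June. The drug then fails the test of having been taken after the first dose and is classed as prior only, even if it was taken until 25 June.

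**7. With the remedy described under the fix.** Of true post-dose events with unknown day in the first-dose month, none is lost, against about 94% now. The price can be seen in a 30-day month: the mean share of days before the dose is (0 + 1 + … + 29)/(30 × 30) = 435/900 = 48.3%. Day-missing events from those days will count as treatment-emergent unless a stop date rules them out.

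**The case against.** **The rule may not be meant for adverse events.** The visible section that refers to SAP 4.3 for partial dates is SAP 5.3, on disease duration. SAP 8.3 and 8.9 do not cite it, and nothing says outright that the treatment-emergent flag uses an imputed date. This stands as a caveat: the consequence is what follows if the SAP is applied as written. It does not remove the gap, because 4.3 is written for all time-dependent variables and no other rule exists. If another rule is intended, it is not prespecified.

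**Few dates will be partial, and the most important events least of all.** This stands. Onset dates must be recorded in the source and the eCRF (Protocol 7.1.2), and missing data are queried (Protocol Appendix L). Patients stay for at least 30 minutes after dosing (Protocol 5.6.1) and are asked about events before leaving (Protocol Table 1 footnotes). Serious events and events of special interest, including severe hypersensitivity, are reported within 24 hours with an onset date (Protocol 7.1.5.3.1 and 7.1.6). A reader might infer that the rule conceals reactions to the first injection; the documents do not support that.

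**The events are not lost.** This stands too. SAP 8.3 provides listings of adverse events, events of special interest, serious events, injection-site events and events leading to early termination, with dates as collected. Listings do not, however, give incidence by arm.

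**The rule is the same in every arm and the summaries are descriptive.** True, and no efficacy result is touched. Absolute incidence is still understated.

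**Conclusion.** The gap is real and its impact is low. Applied as written, SAP 4.3 places a day-missing onset in the first-dose month before treatment for about 97% of dose dates. About 94% of true post-dose events of this kind then leave the adverse event summaries, while remaining in the listings. Both percentages assume first-dose and onset dates spread evenly over the calendar, and both are conditional on the onset day being missing. They must not be read as shares of all adverse events. The documents give no count of partial dates. For scale, one missing event in a planned arm of 80 moves an incidence by 1/80 = 1.25 percentage points.

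A reader might also infer that the whole rule errs towards undercounting. Only the day-missing branch does. The 1 July branch can add events as well as remove them, and year-only onsets should be rare in a 16-week treatment period with visits about every four weeks. The medication classification has the same weakness for day-missing stop dates in the first-dose month.

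**What to change.** Add to SAP 4.3 or 8.3, before database lock:

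- **Adverse events.** If a partial onset date is compatible with onset on or after first dose, and the event's stop date is not before first dose, the imputed onset is the later of the SAP 4.3 date and the first-dose date, so the event counts as treatment-emergent. A partial stop date should be read at its latest possible value for this test; under the present rule it too would move to the 1st and defeat the condition.
- **Medications.** When classing a drug as prior or concomitant, use the earliest possible start and the latest possible stop.

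The cost is a few sentences in the SAP and one derivation each in the adverse event and medication data sets. Collected dates and listings do not change. SAP 2.5.2 already provides for amendments approved before lock, and for unblinding only afterwards, so the change can be made blind.

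The downside is overcounting. About half of the first-dose month's days precede the dose, so some pre-dose events with unknown day will enter the tables. Medication-withdrawal events recorded during washout, with no stop date before the dose, are the obvious case. For a safety summary that is the conservative direction.

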4.4. Study Days and Visits

Study visits are detailed in Table 1.

Table 1: Study Visits

Study period	Screening Period (Up to 5 weeks [17 to 35 days])			Double-Blind Treatment Period (16 weeks)				
	Screening Visit	Phone Contact (Washout)	Baseline Assessment Period	Randomization (Dose 1)	Dose 2	Dose 3	Dose 4	
Visit	V1	Phone Contact	V2 (BAPS Visit)	V3	V4	V5	V6	V7 (EOT/ EOS or ET)
Day and allowed time windows	Week-5 Day -35	Day -33 through Day -15	Day -14 (±2 days)	Day 1	Day 29 ±7 days	Day 57 ±7 days	Day 85 ±7 days	Day 113 ±7 days

BAPS=Baseline Assessment Period Start; EOT=End of treatment; ET=Early termination; EOS=End of Study.

There was a follow-up period (14 weeks) in the Study TV48125-PN-20028 protocol prior to amendment 04. The data collected in the follow-up period will be listed.

Study days will be numbered relative to the first day of IMP administration. The start of treatment (Day 1 at Visit 3) is defined as the date on which a patient takes the first dose of IMP, as recorded on the study drug administration CRF. Days will be numbered relative to treatment start (ie, ..., -2, -1, 1, 2, ...; with day 1 being the first day of IMP administration and day -1 being the day before the first day of IMP administration).

‘Last Assessment’ will be derived for analysis purposes and is defined as the last observed postbaseline data, excluding the follow-up visit. For by-visit summaries, data from the ET visit will be included as one of the visits indicated in the database.

For data collected daily on e-diary, analysis weeks (week 1, week 2, ..., etc.) will be derived for the purpose of efficacy endpoint analyses. Details are provided in Section 6.1.2.

Statistical Analysis Plan

Data collected after week 12 will be included in descriptive summaries but will not be included in any inferential analyses.

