Study procedures, assessments, and administration of the first dose of IMP will occur at Visit 3 (day 1). Patients will return to the study center approximately every 4 weeks (Visits 4, 5, and 6) for blinded administration of the IMP, and for vital signs, efficacy, safety, and blood samples for pharmacokinetic analysis, immunogenicity, and biomarkers at various time points.

Before the Randomization Visit (Visit 3) and during the 16-week double-blind treatment period, patients will record their daily average pain intensity score and daily worst pain intensity score using the PI-NRS in the e-diary every evening between 1800 and 2200 hours. During the 16-week double-blind treatment period, each week, patients will record their sleep score using the PROMIS Sleep Disturbance SF8a once weekly (in the morning) in the e-diary. Patients will be permitted to take acetaminophen as rescue medication (as needed) and record their pain intensity score before taking rescue medication in the e-diary. At least 75% compliance with e-diary recordings on a weekly basis is expected after the randomization visit. Site personnel will monitor patients' compliance that e-diary entry is at least 75% every week during the double-blind treatment period.

At monthly visits during the double-blind treatment period, end-of-treatment (EOT), and at the time points described in [Table 1](#), the IMD, FIQR, EQ-5D-5L, PGIC, PROMIS Physical Function SF12a, PROMIS Fatigue SF8a, HADS, and C-SSRS questionnaires will be completed at study sites. The PROMIS Sleep Disturbance SF8a will be completed weekly by the patient in the morning in the e-diary. Patients who both discontinue treatment and terminate early from the study before completing the 16-week double-blind treatment period will have the EOT/end-of-study (EOS) or early termination (ET) Visit (Visit 7) procedures and assessments performed as soon as possible thereafter. The e-diaries will be collected at the week 16 visit (Visit 7).

The procedures and assessments will include collection of adverse events, concomitant medication information, vital signs, C-SSRS, and samples for pharmacokinetic analysis, biomarker analysis, and immunogenicity analysis at the time points included in [Table 1](#).

Patients who complete all scheduled visits will have final procedures and assessments performed at the EOT/EOS or ET Visit (Visit 7), approximately 4 weeks after administration of the final dose of the IMP (Visit 6).

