Efficacy endpoints (primary, secondary, XXXXXXXXXX) will be derived from subjective pain ratings collected daily using an e-diary. Eligible patients will receive comprehensive training from site personnel on the correct use of the e-diary. Site personnel will also instruct patients on the requirement for timely and daily completion of the e-diary. At least 75% compliance with e-diary recordings on a weekly basis is expected after the randomization visit. Site personnel will monitor patients' compliance that e-diary entry is at least 75% every week during the double-blind treatment period. If weekly 75% compliance is not maintained, a reminder and any other corrective actions, as deemed necessary, will be issued to the patient (Section 3.6.1).

In the following circumstances, the IMP will be discontinued immediately:

1. any increase in ALT or AST to $\geq 3 \times$ the ULN, combined with INR $> 1.5 \times$ the ULN or total bilirubin $> 2 \times$ the ULN
2. any increase in ALT or AST to $\geq 3 \times$ the ULN, which is accompanied by symptoms clearly associated with impaired liver function (eg, vomiting, nausea, fever, rash, eosinophilia) and not deemed related to other diseases (eg, vomiting or nausea triggered by migraine)

3. any increase in ALT or AST to levels ≥ 5 but $< 8 \times$ the ULN, which is persistent for ≥ 2 weeks of repeated measurements
4. any increase in ALT or AST to levels $\geq 8 \times$ the ULN
5. in any case where monitoring of liver enzymes cannot be performed according to the protocol guidance

Patients should be treated with standard of care after discontinuation from IMP or early termination of the study, as appropriate. All protocol-specified procedures/assessments should be performed at the EOT/EOS or ET Visit (Visit 7) (see [Table 1](#)).

Investigators should attempt to obtain information on patients in the case of early termination from the study or discontinuation from IMP (EOT/early termination; see [Appendix B](#)). Results of any evaluations and observations, together with a narrative describing the reason(s) for early termination from the study or discontinuation from IMP, must be recorded in the source documents. The electronic case report form (eCRF) must document the primary reason for early termination from the study or discontinuation from IMP.

See [Appendix G](#) for information regarding how the study will define and address lost to follow-up patients to help limit the amount and impact of missing data.

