- inform patients of study restrictions and compliance requirements
- assess concomitant medication
- review study compliance

- [REDACTED]
- [REDACTED]
- [REDACTED]
- [REDACTED]
- [REDACTED]
- [REDACTED]
- [REDACTED]
- [REDACTED]

- blood sample for serum anti-drug antibody (ADA) concentration
- [REDACTED]
- inquire about adverse events
- [REDACTED] Since Last Visit version
- administration of IMP
- review e-diary

b. Administration of Investigational Medicinal Product (Visits 4, 5, and 6, days 29 [week 4], 57 [week 8], and 85 [week 12] ±7 days, respectively)

For Visits 4 and 5 (when at-home dosing is available), home visits are permitted for patients who are not able to go to the investigational center or if the investigational center staff are not able to see patients at the investigational center.

The following procedures and assessments will be performed at Visits 4, 5, and 6 (days 29 [week 4], 57 [week 8], and 85 [week 12] ±7 days, respectively):

- study assessments/pain reporting training (and as needed, for subsequent retraining throughout the study)
- e-diary data review/training (and as needed, for subsequent retraining throughout the study)
- dispense/account rescue medication
- PI-NRS (recorded daily)
- clinical laboratory tests (Visit 6 [day 85] only)
- urine drug screen
- abbreviated physical examination
- electrocardiography (Visit 6 [day 85] only)
- vital signs measurements
- urine pregnancy test for women of childbearing potential (serum pregnancy test may be completed to confirm, if warranted)
- inform patients of study restrictions and compliance requirements
- assess concomitant medication
- review study compliance
- [REDACTED]
- [REDACTED]
- [REDACTED]
- [REDACTED]

- [REDACTED]
- [REDACTED]
- [REDACTED]
- [REDACTED]
- blood sample for plasma concentration of IMP (Visit 6 [day 85] only)
- blood sample for serum ADA concentration (Visit 6 [day 85] only)
- [REDACTED]
- inquire about adverse events
- [REDACTED] Since Last Visit version
- administration of IMP
- review e-diary

5. End-of-Treatment/End-of-Study or Early Termination (Visit 7, day 113 [week 16] ±7 days)

The following procedures/assessments will be performed at Visit 7 (day 113 [week 16]):

- account/collect rescue medication
- PI-NRS (daily in e-diary) (Note: Collection ends the day before or the morning of Visit 7 if missed the day before)
- clinical laboratory tests
- urine drug screen
- abbreviated physical examination
- electrocardiography
- vital signs measurements

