6. EFFICACY ANALYSIS

6.1. General

The mITT analysis set will be the main analysis set for all efficacy analyses. The PP analysis set will serve as supportive analysis set for analyses of the primary efficacy endpoint and following selected secondary efficacy endpoints:

- responder rate of PGIC rating (percentage of patients much improved or very much improved) at week 12
- change from baseline to week 12 in the weekly average of the daily worst PI-NRS score over the past 24 hours
- the percentage of patients who experience a $\geq 30\%$ reduction in the weekly average of the daily average PI-NRS score at week 12
- the percentage of patients who experience a $\geq 50\%$ reduction in the weekly average of the daily average PI-NRS score at week 12

For efficacy summaries and analyses using the last visit, this last visit should not include the follow-up visit which was scheduled in Study TV48125-PN-20028 prior to protocol amendment 04. In addition, data collected after week 12 will be included in descriptive summaries but will not be included in any inferential analyses.

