6.3. Secondary Efficacy Endpoints and Analysis

The secondary efficacy endpoints are listed in Section 1.1. Analysis will be based on mITT and PP analysis sets.

Missing data for the following secondary endpoints will be imputed using the MI method detailed in Section 6.2.2:

Statistical Analysis Plan

- the percentage of patients who experience a $\geq 30\%$ reduction in the weekly average of the daily average PI-NRS score at week 12
- the percentage of patients who experience a $\geq 50\%$ reduction in the weekly average of the daily average PI-NRS score at week 12
- change from baseline to week 12 in the weekly average of the daily worst PI-NRS score over the past 24 hours

There will be no imputation for missing data for all other secondary efficacy endpoints unless noted otherwise.

6.3.1. Change From Baseline to Week 12 in the Individual Components of the Fibromyalgia Impact Questionnaire Revised: Symptom Subscore, Impact Subscore, and Functional Subscore Score

The FIQR is a commonly used instrument in the evaluation of FM patients. It contains 21 questions in 3 domains: function (9 questions), overall impact (2 questions), and symptoms (10 questions). Questions are graded on a 0 to 10 numeric scale with 10 being the worst. All questions are framed in the context of the **last 7 days**. The sub-total scores (subscores) and total scores will be calculated by ICON using the scoring guidance [[The Revised Fibromyalgia Impact Questionnaire \(FIQR\): validation and psychometric properties](#)] and will be provided in the database. The sub-total score for each domain is the summation of scores in the domain. The function sub-total score ranges from 0 to 90; overall impact sub-total score ranges from 0 to 20; the symptoms sub-total score ranges from 0 to 100. According to the scoring guidance, the FIQR total score is calculated as (the function sub-total score divided by 3) + the overall impact sub-total score + (the symptoms sub-total score divided by 2). Thus FIQR total score ranges from 0 to 100.

The FIQR will be assessed at BAPS visit and visits 3 to 7 (weeks 1, 4, 8, 12, and 16).

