The change from baseline in FIQR symptom sub-score, impact sub-score, functional sub-score, and total score will be analyzed, respectively, using a MMRM method with change from baseline in the FIQR score at weeks 4, 8, and 12 as the dependent variable, sex, age group at FM onset, week, treatment, and treatment by week interaction as fixed factors, and the baseline FIQR score as a covariate. ARH(1) for repeated observations within patients will be used, and the denominator degrees of freedom will be estimated using Kenward-Roger's approximation. Missing total score will be considered as missing at random.

Notes, if ARH(1) does not converge, then simpler covariance structures with less parameters will be used in the following order until the model converges: AR[1]; CSH; and CS.

The LS mean estimates for the mean change from baseline as well as the difference of the estimates between the fremanezumab and placebo group, with the corresponding SE, p-value and associated 95% CI will be provided. The results from all visits will be presented.

SAS codes are:

```
ODS OUTPUT LSMEANS= LS DIFFS = DIFF (WHERE = (AVISIT = _AVISIT));  
PROC MIXED DATA= name;
```

```
CLASS SUBJID TRT01PN AVISIT AGEATFMONSET SEX;
```

Statistical Analysis Plan

```
MODEL CHANGE= BASE TRT01PN AGEATFMONSET SEX AVISIT  
TRT01PN*AVISIT/DDFM=KR;  
REPEATED AVISIT/SUBJECT= SUBJID TYPE= ARH(1);  
LSMEANS TRT01PN*AVISIT / DIFF CL;  
RUN;  
ODS OUTPUT CLOSE;
```

Where AVISIT denotes the study visit/week; BASE denotes the baseline value for the FIQR scores.

In addition, the FIOR scores will be summarized using descriptive statistics for all visits.

6.3.2. The Patient Global Impression of Change Rating at Week 12

The PGIC scale evaluates all aspects of patients' health and assesses if there has been an improvement or decline in clinical status since the start of the study. Patients will record responses to the PGIC scale visits 6 and 7 (weeks 12 and 16). Improvement is recorded on a 7-point scale, with 1 indicating very much improved, 4 indicating no change, and 7 indicating very much worse:

- 1 = Very Much Improved
- 2 = Much Improved
- 3 = Minimally Improved
- 4 = No Change
- 5 = Minimally Worse
- 6 = Much Worse
- 7 = Very Much Worse

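### SAP 4.4 has no study-day rule for early-termination questionnaires, so FIQR, Physical Function and Fatigue ratings from patients who stop before week 12 probably miss the week 4/8/12 models and are tabulated as week 16.

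*SAP*

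**What the plan says.** **Label.** The last column of SAP Table 1 (Section 4.4) is headed "V7 (EOT/ EOS or ET") and placed at day 113 ±7. Protocol Appendix B titles the same visit "End-of-Treatment/End-of-Study or Early Termination (Visit 7, day 113 [week 16] ±7 days"). Neither document gives ET a separate number or week.

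**Timing and content.** The Protocol synopsis has the "early termination (ET) Visit (Visit 7) procedures and assessments performed as soon as possible thereafter", that is, once the patient has left. Protocol 4.3 adds that "All protocol-specified procedures/assessments should be performed at the EOT/EOS or ET Visit (Visit 7"). Protocol Table 1 schedules FIQR, Physical Function and Fatigue in that column.

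**Tabulation.** SAP 4.4: "For by-visit summaries, data from the ET visit will be included as one of the visits indicated in the database". It derives analysis weeks from actual dates only for daily e-diary data (SAP 6.1.2, Table 2).

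**Models.** SAP 6.3.1 states "The FIQR will be assessed at BAPS visit and visits 3 to 7 (weeks 1, 4, 8, 12, and 16"), which makes Visit 7 week 16. It then models "change from baseline in the FIQR score at weeks 4, 8, and 12 as the dependent variable". SAP 6.3.6 and 6.3.7 use the same three weeks for Physical Function and Fatigue. All three sections assume missing at random, and SAP 6.3 rules out imputation for these endpoints.

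**The concern.** A patient who stops for lack of efficacy on day 50 and completes the FIQR on day 53 gives a rating that describes the state in which the patient left. Followed as written, the plan stores it under Visit 7. The model then sees the week-4 score and treats weeks 8 and 12 as missing at random. A patient who stops before Visit 4 contributes no post-baseline value to these models, although one was collected.

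If leaving depends on the score at leaving, that score is what makes missing at random credible. With it in the model, dropout depends on an observed value. Without it, dropout depends on an unseen one, and the model fills the later weeks from patients who were doing better.

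The SAP itself treats such dropout as informative for the primary endpoint: Sections 1.4 and 6.2.2 return patients who stop for lack of efficacy or adverse events to baseline on average. The three questionnaires have no comparable protection. Separately, week-16 descriptive tables would combine day-113 values with values from much earlier days.

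**Working it through.** No figure in the plan is at stake, so the check traces the label and then shows what a window would change.

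**1. Trace of a day-53 ET rating**
- Label available: Visit 7, week 16 (SAP Table 1, Protocol Appendix B). The tablet menu is organised by visit tabs (Protocol 3.6.2).
- Model levels: weeks 4, 8 and 12. Week 16 is not one of them, so the rating is not used.
- By-visit table: week 16, if the database keeps the only label given.
- Last Assessment (SAP 4.4): the rating qualifies, but SAP 6.3.1, 6.3.6 and 6.3.7 name no analysis that uses it.

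**2. Where ET days fall.** Inputs: target days 29, 57, 85 and 113. The midpoints are (29+57)/2 = 43, (57+85)/2 = 71 and (85+113)/2 = 99. The possible ET days are 2 to 112, which is 111 days. Spreading ET evenly over them is an assumption.

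| Nearest visit | ET days | Number | Before that visit's target day |
|---|---|---|---|
| Week 4 | 2–43 | 42 | 27 (days 2–28) |
| Week 8 | 44–71 | 28 | 13 (days 44–56) |
| Week 12 | 72–99 | 28 | 13 (days 72–84) |
| Week 16 | 100–112 | 13 | – |

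Of the 111 days, 42 + 28 + 28 = 98 (88%) are nearer to a modelled week than to week 16. On 27 + 13 + 13 = 53 (48%) the rating would fill a modelled week whose scheduled visit had not yet taken place. On 104 days (2–105) ET precedes the Visit 7 window of days 106–120.

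**3. Week-16 tables.** If a fraction p of the week-16 values come from early stops and their mean is d points worse, the week-16 mean shifts by p × d. With d = 1 and p = 0.1, 0.2 or 0.3 (assumed), the shift is 0.1, 0.2 or 0.3 points.

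**4. Model bias in one arm.** The documents give no dropout rate or FIQR SD. The simulations assumed a change SD of 20, adjacent-visit correlation 0.75, mean changes of −8, −11 and −12, and logistic dropout on the score at leaving with slope 0.5, 1.0 or 1.5 per SD. The week-12 mean was estimated by maximum likelihood with and without that score.

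| Dependence (slope) | ET on the visit day, 13–30% dropout: improvement overstated if ET omitted | ET 14 days before the visit, 14–37% dropout: overstated if omitted | ET 14 days before the visit: understated if slotted |
|---|---|---|---|
| None | – | about 0 | 0.2–0.4 |
| Weak (0.5) | 0.5–1.5 | 0.4–0.9 | 0.4–0.7 |
| Moderate (1.0) | 1.1–2.8 | 1.1–2.2 | 0.6–1.0 |
| Strong (1.5) | 1.7–3.9 | 2.0–3.3 | 1.0–1.5 |

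When ET coincides with the visit it is slotted to, slotting leaves a bias within 0.1. An SD of 20 resembles the FIQR total; the listed endpoints are subscores with ranges 0–90, 0–20 and 0–100 (SAP 6.3.1), so the figures do not carry over directly.

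**The case against.** **The database is not shown.** SAP 4.4 refers to one of the visits in the database without naming Visit 7, and SAP 4.1 lists early-termination visits apart from scheduled and unscheduled ones. A reader might infer that ET ratings certainly appear as week 16; the documents do not prove that. This stands, and it makes the week-16 placement an inference. It does not remove the gap: a separate ET label would also keep the rating out of the week 4, 8 and 12 levels. Only relabelling by date would bring it in, and the SAP states no such rule.

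**The post-week-12 rule.** SAP 6.1 says that "data collected after week 12 will be included in descriptive summaries but will not be included in any inferential analyses". A reader might take this as the exclusion. By date it does not exclude a day-53 rating; the exclusion comes from the visit label and the three model levels.

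**SAP 1.4.** It says that no further efficacy data are collected after discontinuation before week 12. That is written for the primary estimand, but it could mean that ratings after stopping were never meant to be modelled. It conflicts with the ET schedule, so the two need reconciling.

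**The bias is built into the simulation.** Dropout was generated from the score that is then restored. This is fair: the direction is conditional on the dropout mechanism. Slotting is not free either. Under weak dependence, with ET 14 days early, it errs about as much in the other direction.

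**Limited reach.** Average pain, worst pain and the responder rates use diary weeks. Lack-of-efficacy dropout is itself an endpoint. Laboratory and vital-sign tables also give the last assessment. The study has already stopped for futility. All true, and this keeps the point modest.

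**Conclusion.** The point holds as a gap in the mapping rule. On the only label in the documents, FIQR, Physical Function and Fatigue ratings from patients who stop before week 12 are outside their models and inside the week-16 summaries. For stops after week 12, leaving Visit 7 out of the models is by design.

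The week-12 mean in an arm is biased toward improvement if dropout depends on the score at leaving. The illustrations run from 0.4 to 3.9 points over weak to strong dependence, all on assumed inputs; with no dependence the bias is about zero. A reader might infer that the fremanezumab–placebo difference is biased by that amount. The documents do not support this: the figures are for one arm, and equal dropout patterns would cancel. Nor can one conclude that slotting removes the bias, since that needs ET to fall close to the visit. The primary PI-NRS analysis, which uses e-diary analysis weeks, is unaffected. This is a worthwhile, inexpensive correction to three secondary analyses and the by-visit tables.

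**What to change.** In SAP 4.4, before unblinding:

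1. Assign each ET site assessment by actual study day to the nearest scheduled post-baseline visit, with windows cut midway between days 29, 57, 85 and 113 (cut points 43, 71 and 99).
2. If that visit already has an assessment, move the ET value to the next scheduled visit only when the ET day lies within a stated distance of it; otherwise keep it as Last Assessment only. Example: Visit 4 on day 29 and ET on day 40. Week 4 is occupied and day 57 is 17 days away, so the stated distance decides.
3. Set a minimum study day for slotting to week 4. With a 7-day recall, a day-3 rating mostly describes the time before the first dose.
4. Use the slotted values in the FIQR, Physical Function and Fatigue models and in the by-visit tables. Report the unslotted models as a sensitivity analysis.
5. Reconcile the rule with the SAP 1.4 statement that no further efficacy data are collected after discontinuation before week 12.

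If the database already relabels ET by date, state that rule in the SAP instead.

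The cost is a windowing table and a programming step; no new data are needed. SAP 2.5.2 places SAP approval before database lock and unblinding, so the rule can be fixed blind. The downside is that slotted values vary more in timing, and a rating taken well before its assigned visit can slightly understate improvement.
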